It is also imperative to fully pilot both treatments prior to a large trial to assess how they run in real-time from a logistical and practical sense. By piloting these treatments, we will be able to determine how we may need to adjust them to maximise the results. First, the credibility of a sham treatment to people with painful knee OA needs to be evaluated. Our past trials in back pain have used sham education, however, we need to use a sham that is targeted specifically to people with OA and is more realistic. Second, it is key to get feedback from people with knee OA about the Explain Pain intervention so that we can improve it, and its delivery, as much as possible. We have shown that tailoring Explain pain education to the condition (e.g., back pain) has better results²⁰ – this is exciting given that a relatively untailed intervention had excellent effects in knee OA (clinical audit pilot data). We would expect tailored education to be even better.

Aim

To perform a pilot study to assess the feasibility of successfully conducting a randomised controlled trial that investigates the effect of adding Explain Pain (vs adding sham treatment) to an individualised, physiotherapist-led physical activity and general education program in people with painful knee osteoarthritis.

Objectives

The primary feasibility objectives relate to:

- i) Participant eligibility and recruitment
- ii) Participant follow-up
- iii) Objective physical activity measurement (i.e., valid wear time)
- iv) Fidelity of intervention delivery

The primary pilot objectives relate to:

- i) Credibility of the sham intervention
- ii) Acceptability of Explain Pain content and its delivery format (for participants and clinicians)

The secondary objectives are to:

- i) To identify barriers to participation
- ii) Provide estimates of treatment effect (and its variance) for pain and physical activity to inform power calculations for a full-scale RCT

Study Design

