Pilot outcomes: These outcomes will assess participants' and treating clinicians' perspectives on the clinical interventions with the aim to maximise benefit in future studies. These ratings will not inform feasibility of progression to a full trial, but will be used to improve the interventions. Treatment content acceptability/usefulness, treatment delivery acceptability, and sham credibility will be assessed. Agreement with treatment acceptability/usefulness statements will be rated using 5-point Likert scales ranging from "strongly agree" to "strongly disagree" in both participants and clinicians. Sham ultrasound credibility will be assessed in participants using an identical Likert scale.

We will assess the proportion of participants that consider: i) the sham intervention to be a credible treatment; ii) the content of the Explain Pain sessions to be acceptable/useful; ii) the intervention format/delivery to be acceptable. The proportion of participants that "agree" or "strongly agree" with the statements will be calculated. Ratings of acceptability will be taken at 4 weeks, 8 weeks and 6 months. Additionally, acceptability will also be informed by a telephone interview at completion of the trial. For treating clinicians, usefulness/acceptability of the intervention will be rated by evaluating agreement to statements that: i) the delivery of the required Explain Pain content can be feasibly achieved in the time available; ii) the content of the Explain Pain session is acceptable. These ratings will be assessed at 4 weeks and via informal interview at the completion of the trial.

*Note: These primary outcomes will also be evaluated at the interim stage of the feasibility trial – after recruitment of 1/3 of the study participants.

Secondary outcomes:

- To identify barriers to participation (asking eligible participants that decline participation their reason for declining)
- To identify improvements in the delivery or content of Explain Pain Sessions (considering both participants' and treating clinicians' ratings of acceptability) and sham treatment
- To identify any modifications needed in the design of a larger efficacy trial.
- To undertake calculation of an appropriately powered sample for a subsequent RCT using estimates of treatment effect (and its variance) provided for pain, physical activity and function.

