Appendix 16 – Participant Experience Questionnaire

(Credibility – 1, 2, 3; Acceptability – 4, 5, 6; Perceived usefulness – 7, 8, 9, 10)

Consider the following statements and place a tick in the box that best describes your response:

	Strongly disagree	Disagree	Unsure	Agree	Strongly agree
1. I would recommend this treatment to other people with knee osteoarthritis					
2. I had confidence in the expertise of the Physiotherapist who treated me					
3. It was easy to believe what the Physiotherapist told me					
4. I enjoyed attending the treatment sessions					
5. The treatment sessions were relevant to me					
6. It was worthwhile attending the treatment sessions					
7. The treatment sessions have increased my knowledge and understanding					
8. As a result of the treatment sessions I am likely to increase my activity level in the short term (the next 3-6 months)					
9. As a result of the treatment sessions I am likely to increase my activity level in the long term (beyond 3-6 months)					
10. The treatment sessions have changed the way I think about my knee pain					

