Appendix 18 – Clinician Short Answer Questions (Explain Pain Intervention Group only)

Please provide a short answer to the following questions:

1. Briefly describe your experience as the therapist delivering the Explain Pain intervention in this study:

1. Do you think the participant considered the intervention to be an acceptable treatment?
Yes / No (circle). If 'No': please describe any aspects that were not well accepted.

3. Do you have any suggestions for how the CONTENT of the treatment sessions could be improved?

4. Do you have any suggestions for how the FORMAT of the treatment sessions could be improved? (e.g. number of sessions, duration of sessions)

2. Do you have any other suggestions?

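### The participant and clinician forms do not carry the ratings that the pilot outcomes specify, above all a rating of the sham ultrasound itself

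*Protocol*

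**What the plan says.** Section 2 (Objectives) lists "Credibility of the sham intervention" as the first primary pilot objective. Section 3 (Outcomes, Pilot outcomes) sets out how the pilot outcomes are to be measured:

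- For the sham: "Sham ultrasound credibility will be assessed in participants using an identical Likert scale". The result is the proportion of participants in the top two agreement categories.
- For acceptability and usefulness, 5-point agreement scales are to be used by participants and clinicians alike. Participants are to judge session format and delivery as well as content.
- Clinicians are to rate two statements at 4 weeks: that "the delivery of the required Explain Pain content can be feasibly achieved in the time available", and that "the content of the Explain Pain session is acceptable".

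Section 5 (Data Collection) says that the forms are in Appendices 3 to 18. Three of them bear on these outcomes. Appendix 16 is a 10-item participant rating form whose key reads "Credibility – 1, 2, 3; Acceptability – 4, 5, 6; Perceived usefulness – 7, 8, 9, 10". Appendix 17 holds open questions for participants. The only clinician form is headed "Appendix 18 – Clinician Short Answer Questions (Explain Pain Intervention Group only").

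The same Outcomes section says that these ratings serve to improve the interventions and do not decide progression to the full trial.

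**The concern.** The background section argues that the benefit seen in the clinical audit may be non-specific, that a sham comparison is the way to find out, and that the sham's credibility must be established before a large trial. The pilot therefore needs a rating of the sham itself.

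Control participants receive more than the ultrasound. They also get standard osteoarthritis education, discussion of their x-ray, a graded walking program and goal setting, all from the same physiotherapist. If the form asks only about the treatment as a whole and about the physiotherapist, a participant who found the ultrasound unconvincing could honestly agree with every credibility item. The pilot would then report credibility of the package and the therapist under the label of sham credibility.

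Timing adds to this. Adaptations are confined to recruitment of the first third of participants, and the interim evaluation in Section 6 reviews these same questionnaires for credibility. A weak sham could pass that review unnoticed.

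**Working it through.** No figure in the plan is in dispute, so the check sets each defined outcome beside the form meant to supply it.

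| Outcome in Section 3 | Form | What the form holds | Match |
|---|---|---|---|
| Credibility of the sham ultrasound, participant agreement rating | Appendix 16, items 1–3 | Item 1: would recommend the treatment. Item 2: confidence in the physiotherapist. Item 3: believing the physiotherapist | No item isolates the ultrasound |
| Acceptability of format and delivery, participant agreement rating | Appendix 16, items 4–6 | Enjoyment, relevance and worth of the sessions | No dedicated item; format is an open question in Appendix 17 |
| Content can be delivered in the time available, clinician agreement rating | Appendix 18 | Open request for suggestions on format, with session number and duration as prompts | No statement, no scale |
| Content is acceptable, clinician agreement rating | Appendix 18 | One Yes/No question on how the clinician thinks the participant saw the treatment | Different question, different respondent's view, no scale |

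Counting items:

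- Naming the ultrasound: 0 of 10 in Appendix 16 and 0 of 4 in Appendix 17.
- Credibility items: 3, of which 1 rates the whole treatment and 2 rate the therapist or what was said. Item 2 reads "I had confidence in the expertise of the Physiotherapist who treated me".
- Appendix 18: 0 of 5 questions use an agreement scale, 0 of 5 ask whether content fitted the time, and 0 of 5 ask the clinician's own view of content acceptability in rated form.

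What items 1–3 can yield: answered by the 10 to 15 control participants, they give a proportion for the credibility of education, walking program, ultrasound and therapist together. Separating the ultrasound would need an item that refers to it. Comparing items 1–3 between arms does not help, because Section 3 (Treating physiotherapists) assigns each physiotherapist to one arm only. A difference, or its absence, would mix therapist with treatment.

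**The case against.** The best counter-argument is that the protocol often uses sham for the whole control arm. The Sham row of the visit schedule covers all four treatment sessions and the workbook, and the note in the Procedure section speaks of participants receiving sham intervention. On that reading, item 1 answered by control participants is a credibility rating on the promised scale. This stands in part: items 1–3 are usable data on the package. It does not settle the matter. The Outcomes sentence names the ultrasound, the control-arm description presents the ultrasound as the sham treatment, and the Aim treats sham as something added to an activity and education program.

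A second argument is that format and time are covered elsewhere. Participants are asked in Appendix 17 how format could be improved, and a telephone interview informs acceptability. Clinicians are prompted on session duration, consulted at the interim evaluation and interviewed informally at the end. Audio recordings show the proportion of treatments delivered in full, with an 80% threshold in Table 5, which bears directly on whether content fits the session. All of this stands, so a reader who infers that time sufficiency goes unexamined would be wrong. What these sources cannot supply is the agreement rating that the protocol defines. The protocol also refers to the Explain Pain therapist in the singular; if only one clinician responds, the missing rating costs less.

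A third argument is that no decision hangs on these ratings. That is correct for progression. The ratings are nevertheless meant to improve the interventions, and improving the sham needs information about the sham.

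**Conclusion.** The mismatch is real. Three sets of pilot outcomes cannot be reported as defined: credibility of the sham ultrasound, the two clinician ratings, and participant acceptability of format. The first matters most, because it is a primary pilot objective and no later analysis can recover an item that was never asked.

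A reader might go further and infer that these pilot questions cannot be answered at all, that control participants yield no usable data, or that the decision to proceed is compromised. The documents do not support this. Package-level credibility and informal clinician and participant views will be available, and Table 5 contains none of these ratings. Nor do the documents show how highly an unconvincing ultrasound would score on items 1–3; they show only that those items could not reveal it. A formal test of blinding is not a stated objective, so its absence is not counted here.

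The conclusion assumes that the appendices are the complete set of forms, as Section 5 indicates.

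**What to change.** 1. Add an agreement item on the credibility of the ultrasound component and base the sham-credibility proportion on it. Report Appendix 16 items 1–3 as credibility of the package and therapist. The week 4 assessment is in person with the blinded assessor, so the form should look the same in both arms, for example neutral wording that asks about each treatment component with an option for not received. It should be self-completed after the outcome measures and returned unseen by the assessor.
2. Add to Appendix 18 the two clinician statements already worded in Section 3, on the 5-point scale.
3. Add one agreement item on session format and delivery to Appendix 16.

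Failing that, reword the pilot outcomes so that they claim only what the forms measure.

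The cost is a few extra items and an ethics notification. There is also a small risk that an ultrasound item at week 4 prompts suspicion before the outcome assessments at weeks 8 and 26. Holding the item back until week 26 would avoid that, but the interim evaluation, which uses 1-month data, would then not see it.

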
Doing regular physical activity can help to reduce your pain, strengthen your muscles, maintain your joint function and improve your sleep and overall health.
	
3
	
Regular physical activity has countless health benefits (at any age) and enhances bioplastic change in your whole system. This helps make your system less sensitive = able to do more with less pain. There is very strong evidence that activity and exercise are safe and do not lead to further structural damage.
	
3 & 4

It is normal to feel some pain in your muscles when you start an exercise program or new activity. However, if pain feels unusual or severe, or lasts for more than 2 hours after you have stopped, it is probably best to avoid or change that activity.
	
3 & 4
	
Understanding what pain means can powerfully influence pain. It is often not necessary to stop an activity if it is painful. Your own brain can make powerful medications to reduce pain.
	
All

Table 3: Educational topics in the Usual care [standard education] control group and enhanced education provided in the Explain Pain intervention group

Treatment component	Interventions - Graded walking program combined with:		Timing Considerations
	Standard Education + Sham US (Control)	Enhanced education (Explain Pain)	
Session 1			To more closely match treatment duration and therapist time between groups, the Control group will have: 1. Increased time taken for the Standard physiotherapy assessment (go slow!) 2. Inactive ultrasound application
Baseline assessment	Standard physical examination Standard subjective examination	Standard physical examination Enhanced subjective examination ('standard' + identification of participants' education targets for EP).	
Education	General education Provide inactive ultrasound to 4 locations on the most painful knee (~5 mins each). Introduce participants to the AA handbook (to take home)	Enhanced education Introduce participants to 'Explain Pain Handbook' and the 'The Protectometer' (to take home)	
Graded walking program	Instructions for following week re: Establish baseline walking tolerance that does not result in sustained, increased pain following walking (for next session)		

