Feasibility outcomes: Participant recruitment rates will be recorded, including the number of eligible participants that agree to participate and the reasons why participants choose not to participate. The proportion of participants completing the in-person and at-home treatment will be evaluated, as will the proportion of participants with valid accelerometry wear-time (used to assess physical activity levels – see Secondary outcomes below). We will also assess loss to follow-up (% with valid data). Using the audio recorded treatments, we will assess the proportion of the treatments that were completed in full. The following decision making criteria (Table 5) will be used to determine feasibility and the ability to progress to a full RCT.

Progression criteria to proceed to the main trial		
Proceed	Proceed with protocol amendments	Do not proceed
At least 1 adult (on average) per week can be identified as eligible for inclusion	Less than 1 adult per week (on average) can be identified as eligible for inclusion.	Less than 1 adult per fortnight (on average) can be identified as eligible for inclusion.
1 (or more) in 4 eligible participants recruited	At least 1 in 6 eligible participants recruited	Less than 1 in 6 eligible participants recruited
75% or higher follow-up rate at 6 months	At least 50% follow-up rate at 6 months	Less than 50% follow-up rate at 6 months
75% or more of participants randomised to the Explain Group attend at least 3 intervention sessions	At least 50% of participants complete at least 3 intervention sessions	Less than 50% of participants complete 3 intervention sessions
60% or more of at-home treatments are completed	At least 50% of at-home treatments are completed	Less than 50% of at-home treatments are completed.
70% or more of participants have at least 4 days of ≥ 10 hrs of valid wear time (accelerometry)	At least 50% of participants have at least 4 days of ≥ 10 hrs of valid wear time (accelerometry)	Less than 50% of participants have at least 4 days of ≥ 10 hrs of valid wear time (accelerometry)
At least 80% of interventions provided in full (all content covered)	At least 50% of interventions provided in full (all content covered)	Less than 50% of interventions provided in full (all content covered)

Table 5. Progression criteria decision aid to lead to a full RCT.

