The planned primary and secondary outcome measures of a future efficacy trial (and the time-point of assessment in this feasibility trial) are indicated in Table 3. Physical activity level (average daily step count over 7-days measured using wrist-based accelerometry; GT9X Actigraph), average knee pain intensity (0-100 visual analogue scale) and the WOMAC pain and function subscale will be assessed at baseline, after the 4 weeks of clinician-led sessions, at 8 weeks when full treatment is complete and at 26 weeks (6 months). Measures were chosen based on OARSI recommendations for clinical trials of knee OA.²⁹

Table 3. Visit schedule (Rx = treatment; WB = workbook; * = phone call once a week)

Visit	Phone	1	2	3	4	5	6	7
Week	Screen	0	1	2	3	4	8	26
Clinical measures								
Knee x-ray		X						
Physical activity measures		X				X	X	X
Demographic								
Age, gender, OA duration, IPAQ	X							
ACR criteria for OA; FCI		X						
Questionnaires								
Pain VAS, WOMAC		X				X	X	X
PSEQ/ DASS/Fear/PCS/Beliefs		X				X	X	X
Credibility/Usefulness						X	X	X
Intervention								
Real			Rx 1	Rx 2	Rx 3	Rx 4	WB *	
Sham			Rx 1	Rx 2	Rx 3	Rx 4	WB *	

Abbreviations: OA, osteoarthritis; IPAQ, ; ACR, American College of Radiology; FCI, ; VAS, Visual Analogue Scale; WOMAC, ; PSEQ, Pain Self Efficacy Questionnaire; DASS, Distress Anxiety and Stress Scale; PCS, Pain Catastrophising Scale

Sample Size

20-30 participants will be recruited and subsequently randomly allocated to intervention or control groups. This sample size is considered adequate for a feasibility study (designed principally to assess feasibility of recruitment and procedures), and will provide information to inform a sample size calculation for a subsequent randomised controlled trial.

Recruitment

Participants with painful knee OA will be recruited from the community in South Australia via local and national newspapers, Arthritis Australia newsletters, radio advertisements, and social media platforms. At recruitment, participants will be asked about x-rays of their affected knee. If they do not have an xray of their knee, they will not be included.

Procedure (see also Table 2)

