1. Baseline assessment (Visit 1): The study coordinator will contact interested participants by telephone to perform an initial screen and schedule the clinic baseline assessment. At the baseline assessment, written consent will be attained, and demographic information collected (including co-morbidities [Functional Comorbidity Index; FCI]), and all outcome measures assessed (Pain VAS, Western Ontario McMaster Universities OA Index (WOMAC), Pain knowledge/beliefs Questionnaire, Pain Self-Efficacy Questionnaire (PSEQ), Depression anxiety and stress scale (DASS), Brief fear of movement scale for OA, the Pain Catastrophizing Scale (PCS)).

2. Follow-up (Visits 2-): Treatment visits will occur at week 1, 2, 3, and 4. Participants' first intervention visit will be scheduled ~1 week after the baseline assessment to allow for measurement of baseline physical activity levels. Follow-up assessments will occur at week 4, 8, and 26 weeks, and will be performed by the same blinded assessor. Baseline and 4 week assessments will occur in person and 8 and 26 weeks assessments will occur via return reply paid mail-out (paper questionnaires) or via emailing the assessment link (online questionnaires via survey monkey), based on participant preference.

Note: all participants receiving sham intervention will be offered a version of the Explain Pain intervention after the study concludes.

Section 4. Methods: Assignment of Interventions

Allocation

Participants will be randomly allocated (1:1) to intervention groups using a randomisation schedule generated by Excel's randomisation function, using random permuted blocks of 4 and 6. Allocation will be concealed in sequentially numbered, sealed, opaque envelopes created by an investigator not involved in the study data collection or interventions. Eligible patients who have provided informed consent will be allocated to the treatment groups by an independent investigator who will then coordinate treatment appointment scheduling with the appropriate therapist.

Blinding

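### Sham credibility, a primary pilot objective, is first rated at week 4, so early leavers may go unrated and the ratings obtained mix belief in the treatment with perceived benefit

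*Protocol*

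**What the plan says.** The Objectives in Section 2 list "Credibility of the sham intervention" first among the primary pilot objectives. Section 3, Outcomes (Pilot outcomes), defines the measure as the proportion choosing either of the two agreeing categories on a 5-point scale. On timing it says "Ratings of acceptability will be taken at 4 weeks, 8 weeks and 6 months". The visit schedule (the second table numbered 3) has a row "Credibility/Usefulness" marked only at Visits 5, 6 and 7, which are weeks 4, 8 and 26.

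The Procedure section says "Treatment visits will occur at week 1, 2, 3, and 4", so session 4 falls in the week of the first rating. The week 4 assessment is in person. For the later ones, "8 and 26 weeks assessments will occur via return reply paid mail-out (paper questionnaires) or via emailing the assessment link".

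Table 4 gives the control arm its sham at session 1 in the same form as at sessions 2 to 4: "Provide inactive ultrasound to 4 locations on the most painful knee (~5 mins each".

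The Pilot outcomes text also says that the ratings serve to improve the interventions and do not inform progression to the full trial. Section 6 has the experience questionnaires reviewed for credibility and acceptability at the interim evaluation.

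**The concern.** The credibility question is whether participants take the sham as real treatment. It can be asked once the sham has been received, which is at session 1 (week 1). Waiting until week 4 has two possible effects.

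- **Selective loss.** Someone who finds the treatment unconvincing may leave before week 4. If that person leaves the study, or does not return a later form, no rating exists. A proportion among raters then leans towards credible.
- **Mixing with outcome.** This needs no dropout. By week 4 participants have had up to four weekly sessions and a graded walking program, and have felt whether their pain changed. Credibility item 1 of Appendix 16 asks whether they would recommend the treatment, which naturally takes in perceived benefit. The week 8 and 26 ratings come later still.

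At stake is how well the pilot can judge and improve its sham for the future trial. Section 2 justifies the pilot partly by the need to evaluate the sham's credibility in this population.

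**Working it through.** The protocol states no target, power or expected value for credibility, so there is no figure to reproduce. The timing can be read directly; the size can only be illustrated.

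**Timing, from the visit schedule and Table 4**

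| Week | Visit | Treatment | Credibility rated? |
|---|---|---|---|
| 0 | 1 | none | no |
| 1 | 2 | session 1, full sham | no |
| 2 | 3 | session 2 | no |
| 3 | 4 | session 3 | no |
| 4 | 5 | session 4 | yes, first time |
| 8 | 6 | workbook phase complete | yes, post or online |
| 26 | 7 | none | yes, post or online |

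**Illustration in counts.** Input from the registration table: 10 to 15 per arm. Assumptions: 15 in the sham arm, 3 lost unrated (3/15 = 20%), and 11 of the 12 raters agree.

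- Among raters: 11/12 = 91.7%.
- Of those randomised, if all 3 would have disagreed: 11/15 = 73.3%.
- Of those randomised, if all 3 would have agreed: (11 + 3)/15 = 14/15 = 93.3%.

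The range is thus 73% to 93%, around an observed 92%.

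**Illustration as a formula.** Let p be agreement among those who continue, d the share who stop early, and q the share of stoppers who still rate at some point. Assume every stopper would disagree.

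- Proportion among raters = p(1 − d) / [(1 − d) + dq]
- Proportion among all randomised = p(1 − d)

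With p = 0.80 (assumed):

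| d | All randomised | Raters, q = 0 | Raters, q = 0.5 | Raters, q = 1 |
|---|---|---|---|---|
| 10% | 72% | 80% (+8 points) | 75.8% (+3.8) | 72% (0) |
| 25% | 60% | 80% (+20) | 68.6% (+8.6) | 60% (0) |
| 50% | 40% | 80% (+40) | 53.3% (+13.3) | 40% (0) |

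The result depends heavily on q. If all stoppers return a later form, the selective-loss bias is zero. None of p, d and q is given in the protocol.

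**Interim evaluation.** Section 6 triggers it when 1-month data have arrived from 30% of participants: 0.30 × 20 = 6 to 0.30 × 30 = 9, or about 3 to 5 per arm. Hypothetically, with 4 sham participants, one unrated sceptic turns 3/4 (75%) into 3/3 (100%).

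**Mixing with outcome.** No arithmetic applies. Its direction is not fixed: perceived benefit would raise the rating and disappointment would lower it. No planned rating precedes week 4, so the data cannot separate belief from response.

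**The case against.** A reader might infer that participants who stop early never rate the treatment. The protocol does not say so. Ratings belong to the follow-up assessments, not to the treatment sessions, and nothing removes stoppers from follow-up. Two of the three ratings come by post or online. A telephone interview at completion also informs acceptability, withdrawal reasons are recorded when possible, and questionnaire completion rates are calculated, so missing ratings would be visible. This stands, and it limits the selective-loss argument. It does not remove it: the week 4 assessment requires attendance, the closing interview is described for acceptability and not for credibility, and a late form still comes after any change in pain.

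A reader might also take the likely loss from the attendance thresholds in Table 5. The 75% cell names only the Explain Pain group, and attending fewer than three sessions is not the same as returning no form. Table 5 therefore gives no loss figure for the sham arm.

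It can fairly be said that week 4 suits acceptability, because the Explain Pain content is spread over four sessions and x-ray findings are discussed at session 2. That stands, and the point about timing is confined to credibility. The protocol also plans no comparison of credibility between arms, so a biased comparison is not claimed.

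Finally, the denominator and the handling of missing ratings may be left to a statistical analysis plan, and their absence here is no fault. But such a plan cannot supply a session 1 rating that was never collected.

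**Conclusion.** The point holds as a weakness of timing, not as a demonstrated bias. The first credibility rating comes in the week of the last session, about three weeks after the sham is first given in full. The proportion finding the sham credible may be biased upward, and it mixes belief in the treatment with perceived benefit.

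The stronger statement, that the proportion is inflated, is not supported. It needs early loss, loss linked to disbelief, no later return of a form, and a denominator of raters only; the protocol establishes none of these. The 92% against 73% is a hypothetical resting on all four.

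The consequence is moderate. No progression decision depends on these ratings. They do answer a primary pilot objective, guide changes to the interventions and are read at an interim review of very few people. The remedy is cheap enough that the change should be made.

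**What to change.** - Add credibility items 1 to 3 of Appendix 16 at the end of session 1 (Visit 2), in identical, treatment-neutral wording in both arms, completed out of the therapist's sight. No new sham-specific item is needed on this form.
- Report this as the main credibility proportion among all who attended session 1, and show the number randomised beside it.
- Keep weeks 4, 8 and 26 as later ratings.
- Leave acceptability of content and format at week 4, but send the form at the time of stopping to anyone who stops before session 4.

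The cost is a minute or two of participant time at an existing visit. There is a small risk that asking early prompts suspicion under the limited disclosure described in the Blinding section; neutral wording limits it. The resulting proportion may be less favourable.
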